Two-week follow-up. Using Turkprime, all participants will be asked to take an online survey two weeks later (\$2.00 payment). As *secondary aims*, the goal of the follow-up is to assess WTS and recall of ad content, both reactions to warnings⁷², and sustainability of earlier effects. A two-week time frame aligns with other studies on recall of warning labels⁵⁷. Participants will be asked first about their risk appraisals, cognitive and affective beliefs and attitudes about WTS, intention to quit/willingness to try WTS, and among smokers, frequency of WTS during the last two weeks. If a participant has not quit, they will be asked why. If a susceptible engaged in WTS, we will ask why. We will ask all if they saw and responded to WTS ads during the last two weeks (if yes, where), attended social events involving WTS or bought any WTS products – all no/yes. All will be asked to recall content of the two ads they viewed earlier. Analyses of recall will follow the steps by Strasser et al. on cigarette warnings¹⁰³. Based on an MTurk study that used similar methods as proposed¹⁰⁴, we expect 60% - 70% of participants will complete follow-up. We predict stronger sustainability of earlier effects and a higher percent of recall accuracy for warnings in the text + graphic arm than text only arm.

Phase 3 Procedures:

Participants will be stratified by sex and use of other tobacco products (no/yes) and then randomized in a 1:2:2 ratio to the three arms as Phase 2 (control, ads with text warnings, ads with text + graphic warnings). Tasks will be presented (and eye position sampled) using a Tobii T60XL eye tracker, which uses an unobtrusive infrared camera system to sample gaze position at 60 Hz (and with resolution <1 degree of visual angle) while allowing participants free head movement. Each image will be displayed for a fixed time of 10 seconds, during which participants move their head and eyes naturally while looking at the image. The images will consist of the 24 ads, 16 text and 16 graphic warnings from Phase 1. Details of each arm follows.

- *Control arm:* Participants will view the 24 ads from Phase 1 twice in random order without warnings. Further, 16 control non-tobacco ads matched for graphical content, presence of text, people, and other factors will be randomly distributed among these ads.

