We consider this study to involve very minimal risk. Some participants may become alarmed of learning the potential health implications of waterpipe tobacco smoking and the potential for addiction. This may be especially alarming among smokers of other tobacco products (e.g., the perception of the compounding of health risks and potential for addiction using several products). For others, learning of these issues may reinforce existing knowledge.

The benefits of participation, other than the fiscal compensation for completing the entire study (see below), are that participants gain a better understanding of health effects of WTS. The ultimate study goal, and hence benefit to study participants, is to equip them with knowledge that they can use to curb the persuasive appeal of WTS ads, prevent further experimentation with waterpipe tobacco, and achieve cessation to avoid future harm. The benefits of this study also include findings that may lead to policy changes in the regulation of WTS ads from commercial establishments, such as those posed by the FDA.

Data Safety and Monitoring:

This study neither involves the testing of pharmacologic agents nor therapeutic treatments. The primary goal of this study is to examine how the provision of text only or text + graphic health warnings, or lack therefore, on social allure and waterpipe tobacco product ads influence risk appraisals, cognitive and affective beliefs and attitudes about waterpipe tobacco smoking (WTS) and intentions to quit/willingness to try WTS among waterpipe tobacco smokers and susceptible nonsmokers, respectively. This study also examines whether any effects are mediated by reactions to the ads, with a subcomponent to study in more detail attentional factors as potential mediators through use of eye-tracking. Thus, it is classified as a Type 3 Study (Non-therapeutic, non-physical intervention), a minimal risk level study that dictates annual review by the Duke Cancer Center Scientific Monitoring Subcommittee for scientific progress and IRB compliance (*The overall Duke DSMB plan follows the specific details regarding DSMB procedures that will be followed by the research team*).

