Adverse Event Reporting: The study consent form presented on will have a study-related email address and a study toll-free number. In the event a participant emails or calls the toll-free study number, the project manager will record all reported events in the adverse event log (including the subject's name, date, and event description). The project manager will inform the principal investigator, [name]., who will consult with co-investigators as needed on the action that should be taken. This action and date of implementation also will be recorded in the adverse event log. The entire investigative team will participate in classifying events as "serious" or "non-serious (see listing below)," as well as "non-attributable," "possibly attributable" or "attributable" to the intervention (unlike a pharmaceutical trial where known side effects exist, the classification of "expected" vs. "unexpected" is inappropriate for this intervention). *Serious*—any event or condition that is life threatening, results in a

hospitalization, cancer or a physical or cardiac event serious enough to require medical attention. A brief listing follows:

Fatal

Life threatening

Permanently disabling

Required or prolonged hospitalization (Admission—not ER visit)

Overdose

Significant hazard to patient

Non-Serious—all other events.

All adverse events will be reported on an annual basis to the Duke Cancer Center Scientific Monitoring Subcommittee. In keeping with NIH guidelines, minority status and gender also will be included in these reports to allow for detection of differential effects.

Monitoring Safety of Participants

There will be several ongoing mechanisms for monitoring non-medical adverse events. The project coordinator will oversee day-to-day monitoring of the study activities. This monitoring will be facilitated by an email address and a toll-free number provided to participants to report concerns related to study participation. These ongoing progress reports will enable monitoring of the number of participants involved in the intervention groups, attrition rates, and other relevant data.

Mechanisms for Reporting Mon-medical Adverse Events to the Study Principal Investigator and Institutional Review Board (IRB)

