The project coordinator or Principal Investigator will follow up with participants within 48 hours to ensure that the event has been resolved and will document actions taken. Participants will be able to call directly to the study's toll-free number to report non-medical AEs. All non-medical AEs will be reported to the Principal Investigator and to the IRB via annual progress reports.

Mechanisms for Monitoring and Reporting Medical Adverse Events

There are no foreseeable medical adverse events linked to this study. All research projects conducted at or originating from the Duke University School of Nursing are required to have yearly departmental and Institutional Review Board (IRB) review. Reports of AEs are required as part of these progress reports. Additionally, any changes to the project between review periods must be approved by the IRB prior to fielding.

Plans for Assuring Compliance with Adverse Event Reporting

Participants will be instructed to email or call a 24-hour toll-free number if they experience an AE. As mentioned previously, the project coordinator will then inform the Principal Investigator and the IRB as detailed above. All adverse events will be reported to NIDA within 3 weeks of occurrence. Because this study does not include the use of an investigational drug, there is no requirement that the AE be reported to NIDA in real-time. All AEs are reported as part of the progress reports in the non-competitive and competitive renewals.

Plans for Assuring that Action Resulting in Suspension of Trial is Reported

The Principal Investigator will be responsible for contacting NIDA grant program director if any action resulting in temporary or permanent suspension of the trial occurs. Because this trial does not involve any investigational medication, the action would be limited to an IRB- or investigator- initiated suspension.

Plans for Assuring Data Accuracy and Protocol Compliance

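### Adverse events enter the log only if a participant emails or calls, so the reports cannot be relied on to detect differential effects by minority status and gender

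*Combined protocol and SAP*

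**What the plan says.** Under Data Safety and Monitoring, the paragraph on adverse event reporting gives the entry rule: "In the event a participant emails or calls the toll-free study number, the project manager will record all reported events". The log is to hold the subject's name, the date and a description, and later the action taken and its date. The annual reports have a stated purpose: "minority status and gender also will be included in these reports to allow for detection of differential effects".

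The section on monitoring participants' safety opens with "There will be several ongoing mechanisms for monitoring non-medical adverse events". What it then describes is day-to-day oversight by the coordinator, and "This monitoring will be facilitated by an email address and a toll-free number provided to participants to report concerns related to study participation". The section on compliance with adverse event reporting repeats the same route: "Participants will be instructed to email or call a 24-hour toll-free number if they experience an AE".

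The harm foreseen under Risks / Benefits is alarm on learning about health effects and addiction, and for one group the plan adds: "This may be especially alarming among smokers of other tobacco products". In Phase 2 the study already contacts everyone a second time: "all participants will be asked to take an online survey two weeks later". The listed content of that survey covers risk appraisals, beliefs, attitudes, intentions, use, ad exposure and recall. It includes no question about upset or a problem caused by the study, and neither does the list of post-intervention assessments.

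The section on privacy of study records says online data are anonymous and held under a Turkprime ID.

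**The concern.** A spontaneous-report system counts harm multiplied by willingness to report. Here most participants are anonymous online workers paid $2.00 a session, and the foreseen harm is alarm, which few may think worth a call. A short list of reports would then be hard to interpret: it could mean little distress or little calling. A difference between groups could likewise come from a difference in who calls.

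The plan nevertheless gives the reports an inferential purpose, detection of differential effects by minority status and gender. It does not say how someone who calls and gives a name would be matched to an anonymous survey record holding sex and race. What is at stake is what the annual safety reports can support, including any later statement that the minimal-risk judgement was borne out.

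**Working it through.** **1. Routes into the log.** The three safety sections agree: the route is contact made by the participant. The several mechanisms announced come down to coordinator oversight fed by the same email address and phone line. The 48-hour contact follows up an event already reported, so it does not find events. No procedure is written for distress that staff see in the Phase 1 panels or the Phase 3 laboratory.

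**2. Linkage.** The listed log fields do not include sex, minority status, other tobacco use or arm. Phase 2 survey records do hold sex and other tobacco use (stratification factors) and race (a possible covariate), but under a platform ID. The documents describe no bridge between the two.

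**3. Size of the count.** The plan gives no figure on this point, so there is none to reproduce. All rates here are assumptions.
- Phase 2 total: 1000 + 1000 = 2000.
- Assume 5% are upset: 2000 × 0.05 = 100 people.
- Assume 1-10% of them call: 100 × 0.01 to 100 × 0.10 = 1 to 10 reports.

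**4. Information in such a count.** Assume equal numbers of men and women. Given n reports, the number from one sex is Binomial(n, 1/2) if risks are equal and Binomial(n, 2/3) if the risk is doubled. Use an exact two-sided test at 0.05.
- n = 5: the most extreme split has p = 2 × (1/2)^5 = 0.0625, so no result can be significant.
- n = 10: a 9-1 split has p = 2 × 11/1024 = 0.021, and 8-2 has p = 0.109, so only 9-1 or 10-0 rejects. Power ≈ 10 × (2/3)^9 × (1/3) + (2/3)^10 = 0.087 + 0.017 = 0.10; the opposite tail adds less than 0.001.
- The same calculation gives 0.30 at n = 20, 0.53 at 40, 0.81 at 72 and 0.90 at 100.

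**5. Cross-check by a second method.** Take the 1600 people in the two warning arms (800 + 800 over both populations), with true distress of 5% in one group and 10% in the other. The recorded rate is p = true rate × reporting fraction. Normal-approximation power is Φ{[|p1 − p2| − 1.96 √(p̄(1 − p̄)(1/n1 + 1/n2))] / √(p1(1 − p1)/n1 + p2(1 − p2)/n2)}. Group sizes are assumed: 800 and 800 by sex, 320 and 1280 by minority status (20% minority, the share the protocol sets for its panels).

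| Reporting fraction | Expected reports, sex example | Power by sex | Power by minority status |
|---|---|---|---|
| 1% | 1.2 | 0.06 | 0.09 |
| 5% | 6 | 0.13 | 0.16 |
| 10% | 12 | 0.21 | 0.23 |
| 25% | 30 | 0.45 | 0.40 |
| 50% | 60 | 0.75 | 0.62 |
| 100% | 120 | 0.97 | 0.88 |

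The approximation is rough where expected counts are below about 5.

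**6. Bias.** Give two groups of 800 the same 10% distress, with 5% reporting in one and 10% in the other. Expected reports are 800 × 0.10 × 0.05 = 4 and 800 × 0.10 × 0.10 = 8. That is an apparent doubling with no difference in harm.

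**7. Yield of asking everyone at two weeks.** The protocol expects 60-70% to complete follow-up. If upset and completion are unrelated, 5% of 2000 gives 60 to 70 positive answers. The exact test in step 4 then has power 0.66 (n = 60, rejecting at 21 or fewer or 39 or more) to 0.79 (n = 70, rejecting at 26 or fewer or 44 or more). If 2% rather than 5% are upset, even full completion gives only 40 events and power 0.53.

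**The case against.** **The foreseen harm is largely measured already.** Worry about harms belongs to the risk appraisals, a main outcome asked of all Phase 2 participants after exposure and again at two weeks, with arm comparisons planned. Fear appeal is rated for each warning in the Phase 1 pilot. This stands, and it rules out saying that the arms cannot be compared on emotional response. But worry is measured as an effect the warnings are meant to have. It does not record a problem caused by the study or help sought, and it does not feed the log.

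**The purpose clause describes report content, not a powered test.** It is tied to NIH guidelines, so 80% power is not a standard the plan set for itself. This is fair. The power figures show how little such counts can say; they do not show that a promise was broken. The lack of linkage and the dependence on who reports remain whatever standard is used.

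**Solicited items have costs.** A question at the end of the first session would come before the two-week recall and sustainability outcomes, in a study that deliberately avoids drawing attention to the warnings. It could also fill a log in which the whole investigative team classifies each event. This stands, and it is why the item belongs at the end of the two-week survey. As step 7 shows, even that item does not guarantee adequate power.

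**Staff are present in panels and in Phase 3.** They could notice distress, and silence in the text does not forbid logging it. That is so, but no rule says such observations enter the log.

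**Funder reporting.** The plan says "All adverse events will be reported to NIDA within 3 weeks of occurrence", and an event disclosed late may be overdue before the team knows of it. Whether that clock can be changed depends on funder terms that are not in the documents, so it is not pressed here.

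**Conclusion.** The point holds in a limited form. Capture is by spontaneous report only, and the log has no described link to sex or minority status. The reports therefore cannot be relied on for the purpose the plan gives them. At assumed reporting fractions of 10% or less, power for a twofold difference was at most 0.23 in the step 5 table and about 0.10 in the exact test at 10 reports. Unequal reporting can also create a difference where none exists.

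A reader might infer three stronger things that the documents do not support:
- **That counts will be near zero whatever the distress.** No rate is given. With 100 people upset, reporting of 25-50% would give 25 to 50 reports.
- **That the plan promises to compare adverse events between warning arms.** The clause names minority status and gender only. Tabulating by arm would be a useful addition, not a commitment the plan has failed to meet.
- **That participants are at undue risk or that the trial's findings are weakened.** The study is classed as minimal risk with annual review, and no efficacy conclusion depends on these reports.

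This is an inexpensive improvement to the safety reporting, resting on the assumed rates shown.

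**What to change.** Add one item as the last question of the two-week survey, after all outcomes and recall: did taking part cause a problem or upset, how severe was it, and was help sought. Tabulate the answers from the survey data by sex, minority status, other tobacco use and arm. Label the table as description, not as a powered test. Because the answers sit in the survey record, they link to these variables without identifying anyone.

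In the adverse event reporting section, let two further sources enter the log in addition to emails and calls: survey answers that report a problem or help sought, and distress seen by staff in panel or Phase 3 sessions. Reconcile the name field in the log with the statement that online data are anonymous.

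The cost is one survey item and amended wording, plus some extra events to log, classify and follow up. Admitting only reported problems or help sought, rather than worry alone, limits that load. The item reaches only the 60-70% expected to complete follow-up, and those who were upset may be less likely to return, so the result should be reported with the number who answered.

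If the item is not added, replace the purpose clause with a statement that spontaneously reported events will be listed by minority status and gender where known.
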